## **9. Subject's capacity to give legally effective consent: N/A**

## **10. Study Interventions:**

### **Baseline/Pre-Dose Assessment**

After the parent or legally authorized representative has signed the IRB-approved informed consent form, and after it has been determined that the patient satisfies all inclusion and exclusion criteria, the following evaluations will be performed and recorded in the CRF:

1. Baseline demographics, medical history and medical baseline conditions.
2. Physical examination.
3. Preoperative laboratory assessment (obtained as part of usual clinical care for pre-operative assessment:
  - a. Hematology: hematocrit, hemoglobin, white blood cell count with differential, platelet count.
  - b. Serum chemistry: creatinine, blood urea nitrogen, sodium, potassium, calcium.
  - c. Liver function tests: aspartate transaminase (AST), alanine transaminase (ALT), alkaline phosphatase, total bilirubin, conjugated bilirubin, serum albumin.

### **Study Procedures**

1. Record the start and stop time of ambrisentan administration and all concomitant drugs.
2. Hemodynamic evaluation performed during pre-operative cardiac catheterization (obtained as part of usual clinical care), prior to initiation of study drug, and at 0-1,1-6,18-30 and 40-60hrs after administration of the first ambrisentan dose (blood samples will be collected only if central monitoring lines remain or if they can be timed with a routine lab collection)

- a. Record Fontan, common atrial, and systemic arterial pressures from existing central lines that are placed as part of routine post-operative care.
- b. Collect study labs (coincident with scheduled PK levels – see below):
  - i. plasma samples for biomarkers (endothelin 1 [ET1], brain natriuretic peptide [BNP]).
- c. Record oxygen saturation from routinely collected arterial and venous blood gases.
- 3. PK blood samples (500 µL, up to 7 per patient) and pressure measurements will be obtained at baseline and at 1–2, 3–4, 5–6, 8–12, 12–16, 24, and 48 hours post-initial drug administration.
- 4. Adverse events will be collected during and for 1 month after the last study drug administration. Results will be tabulated by organ system.
- 5. Physical examination will be performed within 24 hours after administration of study drug and once daily during study enrollment.
- 6. Record all AEs and SAEs.
- 7. Record all concomitant medication administered 24 hours after administration of study drug.
- 8. Up to 4 scavenge samples will be obtained from the clinical laboratory from samples collected in the 24 hours following ambrisentan administration. Scavenged samples are left over heparinized plasma samples from these children that are collected from the clinical laboratory prior to discarding.

### **PK Sampling**

A limited PK sampling scheme will be employed such that no more than 3000 µl of blood is obtained.

### **Hospitalization Procedures**

- 1. Any of the following clinical laboratories performed as standard of care during the study will be recorded. We will use the laboratory values closest to study dose if there have been multiple tests.
  - a. Hematology: hematocrit, hemoglobin, white blood cell count with differential, platelet count
  - b. Serum chemistry: creatinine, blood urea nitrogen, sodium, potassium, calcium
  - c. Liver function tests: aspartate transaminase (AST), alanine transaminase (ALT), alkaline phosphatase, total bilirubin, conjugated bilirubin
- 2. Physical examination will be performed daily during the post-operative hospitalization.
- 3. Record all AEs for 24 hours after the last dose of study drug
- 4. Record all SAEs for 1 month after the last dose of study drug
- 5. Record duration of mechanical ventilation
- 6. Record hospital length of stay
- 7. Record intensive care unit length of stay
- 8. Record duration and volume of chest tube drainage

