## 4. Design and Procedures

This is a single-center, randomized, blinded PK study of ambrisentan in children ages  $\geq 24$  months and  $\leq 120$  months with single ventricle anatomy. There will be up to 20 subjects enrolled; 16 will receive ambrisentan and 4 will receive placebo. A small placebo control group is warranted to ensure that any treatment effect is not a result of post-operative improvement. Patients will be enrolled at the time of their routinely scheduled Fontan surgery.

**Initial Dose:** Oral ambrisentan 2.5 – 5 mg, single dose, once daily (nasogastric and gastrostomy tube administration will be considered only when a nasogastric or gastrostomy tube is already in place as part of routine post-operative care). Subjects will be randomized by Investigational Drug Services (IDS) to placebo (n=4) or oral ambrisentan (n=16) using permuted blocks. Subjects will receive either an oral suspension (2.5 or 5mg) or a 5mg tablet depending on their ability to swallow a tablet. To begin to ensure safety, the initial 5 subjects enrolled in the study (at least 4 active drug) will receive a dose of 2.5mg in a liquid suspension prepared by IDS. After enrollment of these subjects we will perform a preliminary PK/safety analysis and evaluate ambrisentan exposure. If the drug is well tolerated (no grade III or greater adverse events) and exposure is less than the target exposure of 500-800ng/mL, then we may increase the dose to 5mg/dL provided via tablet in those able to take a tablet or suspension for all others. If drug exposure is less than 100ng/mL then we will enroll additional study subjects to ensure that at least 16 study subjects achieve adequate drug exposure. If drug exposure is in the target range then we will continue to enroll study subjects to receive the 2.5mg suspension.

As summarized below, study drug will be discontinued for any grade 3 or greater adverse event. If this occurs then IDS will be permitted to unblind the study patient to allow for appropriate adverse event reporting. Drug administration will start on post-operative day #1 with initiation of oral feeds. Study drug/placebo will be prepared and delivered to the patient bedside by investigational drug services and administered orally. Subjects will continue on study drug for 3 days.

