Long term ambrisentan use has been associated with a mean lowering of hemoglobin of 0.8mg/dL. These changes have not been seen until after several weeks of therapy. In the post-operative setting it is not uncommon to see some blood loss after surgery. We will monitor daily labs obtained as part of routine post-operative care. If there is a decline in hemoglobin beyond that expected as part of the normal post-operative course, then we will consult with the physicians caring for the child and discontinue ambrisentan if use is possibly contributing to worsening anemia.

**Other risks:** Subjects will be closely monitored in an ICU setting during the first drug administration. They may be transferred to the floor service for the 2nd and 3rd doses but will continue to be monitored with routine vital signs.

**Drug interactions:** Ambrisentan has the potential for drug interactions with cyclosporine

**Potential for benefit:** Ambrisentan is a selective pulmonary vasodilator with potential benefit in this patient population. Use in the post-operative setting may improve post-operative course with the potential to decrease duration of chest tube drainage as well as ICU or hospital length of stay. Whatever the findings may conclude, this study will provide additional information about ambrisentan to physicians and may provide preliminary data for a multi-center pK study in this population. Therefore, future children may benefit from the increased knowledge of physicians who treat them. Participation in this research study is optional; if parents decide not to allow their child to participate in the study their child's routine standard of care will not be altered.

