## **14. Data & Safety monitoring:**

Laboratory data, such as hematology and serum chemistry data will be tabulated by dosage group. Summary statistics for changes from baseline will be presented. Hemodynamic measurements will be described using univariable descriptive statistics (mean median, etc.); observed values and changes from baseline will be summarized.

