### **Study termination**

Adverse events will be defined based on the Common Terminology Criteria for Adverse Events (CTCAE) v4.03 (1).

In accordance with the CTCAE guidelines, adverse events will be evaluated by organ system and broadly defined as follows:

- Grade 1: Mild; asymptomatic or mild symptoms; clinical or diagnostic observations only; intervention not indicated.
- Grade 2: Moderate; minimal, local or non-invasive intervention indicated; limiting age appropriate instrumental activity of daily living.
- Grade 3: Severe or medically significant but not immediately life threatening; hospitalization or prolongation of hospitalization indicated; disabling; limiting self care ADL.
- Grade 4: Life threatening consequences; urgent intervention indicated.
- Grade 5: Death related to AE.

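### The laboratory tables use the value closest to study dose, with no dose, window or direction named and no worst post-dose value planned, so recorded nadirs and peaks may not appear in them

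*Combined protocol and SAP*

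**What the plan says.** Four places bear on this.

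- Section 10, Hospitalization Procedures, first sets the scope of collection: "Any of the following clinical laboratories performed as standard of care during the study will be recorded". The list covers hematology, serum chemistry and liver function tests. The next sentence is the selection rule: "We will use the laboratory values closest to study dose if there have been multiple tests".
- Section 14 describes the output: "Laboratory data, such as hematology and serum chemistry data will be tabulated by dosage group", and then "Summary statistics for changes from baseline will be presented". It names no worst post-dose value, shift table or graded laboratory table, and neither does any other section.
- Section 10, Baseline/Pre-Dose Assessment, takes the baseline laboratory tests before surgery, from usual care. Section 4 starts study drug on post-operative day 1 and adds: "Subjects will continue on study drug for 3 days".
- The Risk/Benefit assessment, in discussing hemoglobin, relies on the full series: "We will monitor daily labs obtained as part of routine post-operative care".

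**The concern.** Safety is part of the primary objective (Section 2). A laboratory safety table should show how far each child's values moved after exposure. The rule selects by closeness in time to a dose, which is a different criterion from severity and may favor a value drawn when the drug has had little time to act. As worded, it even allows a value drawn before dosing.

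The preoperative baseline adds to this. If the dose meant is the first one, the tabulated change runs from before surgery to about post-operative day 1. It could then describe mainly the operation, with little or no drug exposure in it. Later nadirs and peaks would sit in the case report forms but not in the table, and a child tested more often would have more values set aside. The series watched at the bedside and the series reported would also differ.

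**Working it through.** The plan states no sample size, power or error rate for laboratory safety, so there is no figure to reproduce. The check compares the passages and then adds one illustration on stated assumptions.

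**1. What the rule leaves open.** There are 3 daily doses. The rule does not name the dose, the window, the direction (before or after), or whether repeated tests are counted per stay, per dose or per day.

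| Reading | Values used per child and analyte | What the table can miss |
|---|---|---|
| One for the whole course, nearest the first dose | 1, possibly pre-dose | Everything later |
| One per dose | Up to 3 | Values between those chosen, and everything after the one nearest the third dose |
| One per day | A daily series through dosing | Extremes within a day; later days are not addressed |

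No reading guarantees that the worst post-dose value is tabulated.

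**2. Illustration of size (assumptions not in the documents).** Suppose a child has k post-dose values that are exchangeable, and one is chosen by timing alone.

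- Chance that it is the worst = 1/k.
- If the values are also independent and normal, the worst lies on average e(k) within-child standard deviations beyond the chosen one, where e(k) is the expected maximum of k standard normal values. For example, e(2) = 1/√π = 0.56 and e(3) = 3/(2√π) = 0.85.

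| k | Chance that the chosen value is the worst | Average shortfall (within-child SD) |
|---|---|---|
| 2 | 50% | 0.56 |
| 3 | 33% | 0.85 |
| 4 | 25% | 1.03 |
| 6 | 17% | 1.27 |

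If one post-dose value is kept for each of 3 doses, the chance rises to 3/k for k of 3 or more: 3/4 = 75% for k = 4 and 3/6 = 50% for k = 6. Values after surgery are likely to trend, so exchangeability is only a reference case. A trend could move these chances either way.

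**3. Whether adverse event reporting closes the gap.**

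- Study termination (Section 14) defines adverse events by CTCAE v4.03, but nothing says that each laboratory value will be graded.
- Hospitalization Procedures records adverse events to 24 hours after the last dose and serious ones to 1 month. Study Procedures, in the same section, says 1 month for adverse events. Serious events are defined as Grade 3 or greater.
- Under the 24-hour window, a laboratory change below Grade 3 that first appears more than 24 hours after the third dose would not be in the adverse event listing. Under the first two readings above it need not be in the laboratory table either.
- The peer safety review after 6 subjects covers serious events, adverse events possibly or probably related to drug, and early discontinuations. Laboratory data are not listed.

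The backstop is therefore partial.

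**The case against.** The strongest reply is that nothing is lost. A reader might infer that the extremes are dropped from the safety data. The documents do not support that: the sentence before the rule says these tests will be recorded, and the rule governs which value is used. A marked abnormality can also reach the safety data as a CTCAE-defined adverse event, and hemoglobin is watched daily. This stands, and it limits the point to the laboratory tables.

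A reader might also infer that the tables are biased toward showing no drug effect. That is not shown. Section 14 does not say outright that the value selected in Section 10 feeds its summaries, although that is the natural reading. The documents give no time course for transaminases or creatinine. Against a preoperative baseline, the value nearest dose may already carry a large surgical change, so the direction of any distortion is unknown.

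Hemoglobin is also a weak example. The Risk/Benefit assessment says its decline has appeared only after several weeks of therapy and that blood loss after surgery is not uncommon, while dosing lasts 3 days. This stands too, but the selection problem applies equally to the other listed analytes.

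Finally, the tables are descriptive in a pilot with 16 children on drug and 4 on placebo. That limits attribution to drug. It does not explain why values already collected should be left out.

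**Conclusion.** The point holds as a gap in specification and reporting. The rule names no dose, window or direction, and no worst post-dose summary is planned. Recorded nadirs and peaks may therefore be missing from the laboratory tables, and the value used may reflect little or no exposure.

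The omission is possible, not certain: the closest value may be the worst, and a per-dose or per-day reading keeps more of the series. On the exchangeable reference case, a single value chosen by timing is the worst in 50% of children with 2 post-dose tests and 17% with 6. These are illustrations, not estimates from the trial. The conclusion rests on the rule feeding the Section 14 tables, which is an inference. The documents do not support a claim that data are discarded or that the bias runs in a known direction. The change is worth making because it is cheap and uses values already to be recorded.

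**What to change.** In Section 10, Hospitalization Procedures, limit the closest-to-dose rule to choosing the last value before the first dose. State that all routine-care values of the listed tests are kept, with date and time, from the first dose to discharge.

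In Section 14, add for each child, summarized by arm:

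- the worst value after the first dose for each analyte (lowest hemoglobin, platelets and white cells; highest ALT, AST, bilirubin and creatinine);
- its change from both the preoperative baseline and the last pre-dose value, so that change across surgery is shown apart from change after dosing;
- its CTCAE v4.03 grade, where one is defined;
- the number of post-dose tests, and how many children have none.

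The two adverse event windows in Section 10 (24 hours and 1 month) contradict each other and need to be reconciled.

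The cost is some extra date and time entries and one more table. No blood draw is added, and neither sample size nor treatment changes. Worst values will look slightly less favorable in children tested more often, which is why the number of tests should be shown beside them. With 16 versus 4 children soon after surgery, the table should be labelled descriptive: it cannot by itself attribute a change to the drug.

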### **Plasma PK Sampling and Handling**

Timing of samples will treat the start time of oral administration of the first dose as time zero (0). The date and time will be recorded for the start/stop time of oral drug administration and for the acquisition time of the PK sample. The pharmacokinetic samples will be obtained in sodium heparin collection tubes.

## **11. Trial registration:**

The trial will be registered on clinicaltrials.gov before study enrollment begins pursuant with FDAAA trial registry requirements.

## **12. Risk/Benefit assessment:**

Blood volume: In order to minimize the amount of blood sampling, hematology and chemistry laboratory measures will be obtained per local standard of care; and a limited PK sampling scheme will be employed such that no more than a total of 3000  $\mu$ l of blood is obtained from each patient for PK analysis. Blood samples will be collected in 500  $\mu$ L aliquots. In addition a total of 4 samples will be obtained for biomarker assessment. Blood samples will again be collected in 500  $\mu$ L aliquots. No more than 2000  $\mu$ l will be collected for biomarker assessment. During the study samples will be obtained from indwelling central venous catheters. If central venous lines are not available then samples will be obtained from a peripheral IV if present. If no IV is present then every effort will be made to time the PK sampling with line draws or heel sticks for normal laboratory monitoring including chemistries, blood gases, and accucheks. This should result in 1 or 2 additional line draw or possibly heel sticks specifically for PK sampling in any given child.

Drug related adverse effects:

Below is a summary of adverse events associated with ambrisentan use from the pivotal trials as reported on the drug label:

Long term ambrisentan use has been associated with a mean lowering of hemoglobin of 0.8mg/dL. These changes have not been seen until after several weeks of therapy. In the post-operative setting it is not uncommon to see some blood loss after surgery. We will monitor daily labs obtained as part of routine post-operative care. If there is a decline in hemoglobin beyond that expected as part of the normal post-operative course, then we will consult with the physicians caring for the child and discontinue ambrisentan if use is possibly contributing to worsening anemia.

**Other risks:** Subjects will be closely monitored in an ICU setting during the first drug administration. They may be transferred to the floor service for the 2nd and 3rd doses but will continue to be monitored with routine vital signs.

**Drug interactions:** Ambrisentan has the potential for drug interactions with cyclosporine

**Potential for benefit:** Ambrisentan is a selective pulmonary vasodilator with potential benefit in this patient population. Use in the post-operative setting may improve post-operative course with the potential to decrease duration of chest tube drainage as well as ICU or hospital length of stay. Whatever the findings may conclude, this study will provide additional information about ambrisentan to physicians and may provide preliminary data for a multi-center pK study in this population. Therefore, future children may benefit from the increased knowledge of physicians who treat them. Participation in this research study is optional; if parents decide not to allow their child to participate in the study their child's routine standard of care will not be altered.

## **12. Costs to the subject and compensation:**

The subject will incur no charges or fees for participating in the study. Gilead will supply the study drug. The remaining study costs will be covered by the Gilead Sciences Research Scholars Program in Cardiovascular Disease, including cost of pK and biomarker analysis.

## **13. Data Analysis & Statistical Considerations:**

There will be up to 50 subjects enrolled and receiving drug in this study. Additional subjects will be enrolled to ensure that at least 20 subjects have at least 4 evaluable PK samples and that at least 16 subjects have ambrisentan peak exposure > 100ng/dL. Subjects who have only 1 evaluable sample will be included in the analysis. Descriptive statistics such as number of observations, mean, median, 95% confidence interval, standard deviation, standard error, minimum, and maximum will be presented for continuous variables (such as age, weight, etc.). Other descriptive statistics such as counts, proportions, and/or percentages will be presented to summarize discrete variables (such as race, sex, etc.). Pharmacokinetic parameters will be calculated using non-compartmental analysis using WinNonlin software (Pharsight Corporation, Mountain View, CA). As previously mentioned, there will be an interim PK analysis that may alter the dosage.

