**NCT02080637**

**Document Date: March 21, 2016**

**Title: Safety, Pharmacokinetics (PK) and Hemodynamic Effects of Ambrisentan in Single Ventricle Pediatric Patients.**

**1. Protocol Synopsis**

|   |  |
|---|--|
| Protocol Title                     | Safety, Pharmacokinetics (PK) and Hemodynamic Effects of Ambrisentan in Single Ventricle Pediatric Patients.  |
| Product                            | ambrisentan  |
| Objective:                         | To evaluate the safety, PK and hemodynamic effect of ambrisentan in pediatric patients with single ventricle heart defects.  |
| Study Design:                      | Randomized, double blind, placebo controlled PK, safety, and hemodynamic efficacy study.   |
| Study Population:                  | Up to 20 patients ages $\geq$ 24 months and $\leq$ 120 months with single ventricle cardiac lesions; Undergoing elective Fontan surgical palliation.   |
| Number of Subjects:                | Up to 20 subjects  |
| Duration of Subject Participation: | Until 1 month after administration of the last study drug administration   |
| Inclusion criteria                 | 
 
1. Age <math>\geq</math> 24 months; <math>\leq</math>120 months.
 
2. History of congenital heart disease with severe hypoplasia of a right or left ventricle.
 
3. Undergoing Fontan surgery as part of standard clinical care.
 
4. Availability and willingness of the parent/legally authorized representative to provide written informed consent and, as appropriate, assent from the child.
 
  |

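### Section 13 has up to 50 children dosed where the synopsis and Section 4 enrol up to 20; no maximum covers the low-exposure additions, and the exposure cut-off is printed 100-fold too low to match Section 4

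*Combined protocol and SAP*

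**What the plan says.** Four parts of the document bear on how many children enter the study.

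- **Synopsis:** the number of subjects is "Up to 20 subjects".
- **Section 4 (Design and Procedures):** "There will be up to 20 subjects enrolled; 16 will receive ambrisentan and 4 will receive placebo". Allocation is by fixed numbers: "Subjects will be randomized by Investigational Drug Services (IDS) to placebo (n=4) or oral ambrisentan (n=16) using permuted blocks". The same section ties a study duration of about 24 months to enrolling at most 20. It then opens the total upward: "If drug exposure is less than 100ng/mL then we will enroll additional study subjects", the purpose being "to ensure that at least 16 study subjects achieve adequate drug exposure".
- **Section 7 (Subject recruitment):** 50 is the upper limit on the number consented, and 20 is the upper figure for evaluable subjects.
- **Section 13 (Data Analysis & Statistical Considerations):** "There will be up to 50 subjects enrolled and receiving drug in this study". Enrolment continues until "at least 20 subjects have at least 4 evaluable PK samples and that at least 16 subjects have ambrisentan peak exposure > 100ng/dL".

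On units, Section 4 gives the low-exposure trigger in ng/mL. Sections 4 and 5 give the target range as 500–800 ng/mL. Section 13 alone uses ng/dL.

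**The concern.** These sentences decide how many post-operative children aged 2 to 10 years are dosed and when enrolment ends. Section 13 attaches the figure 50 to children who receive drug, whereas Section 7 attaches it to children whose parents consent. These are different populations. Consent is taken before surgery, but raised atrial pressure at the time of drug initiation bars enrolment (Section 12, risk/benefit assessment), so the plan itself allows for consented children who are never dosed.

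Section 4's provision for additional subjects has no upper limit and no allocation rule. A reader cannot tell whether additions may run as far as 50, or whether they are randomised or simply given ambrisentan.

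The exposure cut-off determines whether a subject counts towards the 16. If its unit is wrong, the rule that triggers further enrolment does not work as intended.

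**Working it through.** There is no power-based sample size to reproduce. The check is of totals, of the replacement rule and of units.

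**1. Totals.** Section 4's arms add up: 16 + 4 = 20, which agrees with the synopsis and with Section 4's statement on duration. Section 13's figure does not agree: 50 / 20 = 2.5.

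| Place | Population named | Upper figure |
|---|---|---|
| Synopsis | subjects | 20 |
| Section 4 | enrolled (16 + 4) | 20, plus low-exposure additions of unstated number |
| Section 7 | consented | 50 |
| Section 7 | evaluable | 20 |
| Section 13 | enrolled and given drug | 50 |

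Consent limits dosing to 50 in any case. The maximum that includes additions therefore lies somewhere between 20 and 50, and the document does not say where.

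**2. The replacement rule.** Inputs: 16 planned on ambrisentan (Section 4) and at least 16 required with adequate exposure (Sections 4 and 13). If k of the planned 16 have low exposure, 16 − k are adequate, so at least k more children must receive ambrisentan and the total is at least 20 + k. For k = 1: 16 − 1 = 15, which is below 16, so the total is at least 21. There is no slack.

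Allocation affects the count. If additions are randomised, some will receive placebo, and more than one addition may be needed per low-exposure child. If all additions receive ambrisentan, they are not randomised. The fixed numbers in Section 4 (16 and 4) cover neither case.

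**3. Per subject or per group.** Section 13 counts subjects whose own peak exceeds the cut-off. Section 4's trigger follows the analysis of the first five subjects and could be read as a group result. On the group reading a single low value need not trigger additions. Once the trigger is met, however, Section 4 still counts up to 16 adequately exposed subjects, and the total again has no stated limit.

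**4. Units.** 1 dL = 100 mL, so 100 ng/dL = 100 / 100 = 1 ng/mL. Against Section 4's 100 ng/mL the ratio is 100 / 1 = 100. Relative to the target range:

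- 1 ng/mL is 1/500 = 0.2% of the lower bound and 1/800 = 0.125% of the upper bound.
- 100 ng/mL is 100/500 = 20% and 100/800 = 12.5%.

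Read literally, Section 13 would count as adequate a peak just above one five-hundredth of the lower target bound.

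**The case against.** The strongest reply is that both discrepancies have an obvious origin. Section 7 suggests that 50 is the consent limit carried loosely into Section 13. The unit looks like a typing slip: every other ambrisentan concentration is in ng/mL, both rules use the number 100 and count to 16, and Section 4 elsewhere prints a dose with a per-decilitre unit. I accept both explanations as likely. They account for the text without correcting it, and neither supplies the missing maximum.

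Four stronger readings are tempting, and the documents do not support them.

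- *Two hard ceilings, 20 and 50.* Section 4 itself enrols beyond 20 when exposure is low, so staff following it would not necessarily stop at 20. The defect is a contradictory figure together with an unstated maximum.
- *Staff would in practice apply 1 ng/mL.* This does not follow, since the slip is easy to recognise. How many measurable peaks would pass at 1 ng/mL also depends on an assay limit that the document does not give.
- *The target of 20 PK-evaluable subjects cannot be met with 20 randomised.* The 20 and 16 in Section 13 mirror the 20 in total and 16 on ambrisentan in Section 4, and the sampling schedule in Section 10 does not exempt placebo subjects. Read that way, 20 randomised can meet the target if none is lost. Section 13 also keeps subjects with fewer samples in the analysis: "Subjects who have only 1 evaluable sample will be included in the analysis".
- *A probability that enrolment passes 20.* The document gives no low-exposure rate, and the dose may change after the first five subjects, so one constant rate across all 16 would not describe this design.

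**Conclusion.** The concern holds. As printed, Section 13's number receiving drug is 2.5 times the enrolment in the synopsis and Section 4, and no section states a maximum that includes low-exposure additions. That an addition would be needed after a single low-exposure child rests on Section 13's per-subject wording and on the planned 16 on ambrisentan; it needs no assumption about how often low exposure occurs.

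The cut-off is 100-fold below Section 4's as printed. It is almost certainly a slip, but taken literally it would largely disable the rule that contains it.

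The consequence is confined to the number of children who may be dosed and the point at which enrolment stops. The planned analysis is descriptive, so no power or error-rate claim is affected. Because a sample size and a decision threshold are wrong as written in an enrolment rule, and correction is cheap, they should be corrected.

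**What to change.** Reconcile the synopsis and Sections 4, 7 and 13:

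1. State 50 as the upper limit on the number consented, and remove it as a number dosed.
2. Give one maximum number randomised and dosed that includes any low-exposure additions, and use it in every section.
3. State how additions are allocated between ambrisentan and placebo.
4. Print one exposure threshold in one unit, consistent with the ng/mL of Sections 4 and 5, and say whether it applies to each subject or to the five-subject group.

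The cost is wording only, with one choice for the sponsor. If low-exposure subjects are to be replaced, the stated maximum must exceed 20, which means openly planning for more children dosed. If the maximum stays at 20, the provision for additions in Sections 4 and 13 has to be withdrawn, and 16 adequately exposed subjects can no longer be assured.
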